3.7.1.2 Additional Analyses for Primary Measurement

Besides the primary endpoint analysis, other analyses will be performed based on HRSD measurements.

3.7.1.2.1 Durability of Remission

The durability of remission is the subjects in each treatment group who sustain “remission” from depression after 24 weeks post-treatment at the end of the follow-up phase. “Remission” is assessed by a HRSD score ≤ 10 at the end of the follow-up phase. The null hypothesis is that there is no difference between the treatment and sham groups in the time to recurrence of subjects who sustain remitted after 24 weeks

post-treatment at the end of the follow-up phase. If a subject is no longer remitted at a certain follow-up time point t based on the criteria, then the subject fails and the failure time is the study day of failure (X_{ij}). Durability is calculated by subtracting the date which the subject first becomes remitted from the date of recurrence. Similarly, if a subject remains remitted at a certain follow-up time point, then the subject is censored and the censoring time (C_{ij}) is the date of censoring minus the study day on which the subject became remitted. Group differences will be tested based on the Log-rank test (Mantel 1966). Both Kaplan-Meier estimates (Kaplan and Meier 1958) and the Log-rank statistics will be obtained using PROC LIFETEST (Tables 3.7.2a-c). The survival distribution of durability of remission between the two treatment groups will be plotted using Kaplan-Meier curves (Figures 3.7.2a-c).

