2.3 Study Design

This study is a phase II, randomized and balanced within each stratum, double-blind, sham-controlled, intent-to-treat, 2-arm, parallel design, multicenter study in the United States. Three hundred and sixty veterans diagnosed with TRMD are targeted to be enrolled at 9 VA Medical Centers over a three year period. Participants are randomized into a double blind clinical trial to left prefrontal rTMS treatment or to sham (control) rTMS treatment (1:1 ratio) for up to 30 treatment sessions. All participants are evaluated on a wide variety of measures including cognitive, neurological and functional parameters. All will meet DSM-IV criteria for Major Depression and all will

have failed at least two prior pharmacological interventions as defined by the Antidepressant Treatment History Form (ATHF) (Sackeim et al. 1990), i.e., they are TRMD patients. Veterans with PTSD or history of substance abuse are not excluded but detailed histories regarding these disorders are obtained. Participants are not required to stop using anti-depressant medication. The primary dependent measure is remission rate of Hamilton Rating Scale for Depression ($HRSD24 \leq 10$), and secondary analyses will be conducted on other depression and neuropsychological indices. Comparisons between the rTMS (active) and the sham groups will be made at the end of the acute treatment phase to test the primary hypothesis. The overview of the experimental design and procedures is presented in Appendix 5.1.

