2.5.3. Efficacy Assessment

2.5.3.1. Hamilton Rating Scale for Depression (HRSD)

This measure is the primary outcome measure and is completed after each block of 5 sessions throughout the study. The HRSD is the "gold standard" of

randomized clinical trials for depression, and the primary measure of most rTMS studies to date. This study will utilize the 24-item version of this instrument (HRSD24) to evaluate depressed mood, vegetative and cognitive symptoms of depression, and comorbid anxiety symptoms. It provides ratings on current DSM-IV symptoms of depression, with the exceptions of hypersomnia, increased appetite, and concentration/indecision. The Planning Committee, in making this recommendation, examined the outcome measures used in current NIH and industry trials as well as the ACNP criteria for “remission” (Rush et al., 2006). The ACNP recommends that outcome measures reflect all major criteria used in the diagnosis of MDD. Neither the HRSD or the MADRS include all criteria however, they are widely used in clinical trials and the ACNP report notes that the field has not followed this recommendation and that if one were to use these measures for reasons of comparability (as this Planning Committee recommends), the ACNP report suggests the use of other metrics to assure that remission is complete. For that reason, the Planning Committee recommended additional use of the Quick Inventory of Depressive Symptomatology (QIDS-C16), which meets the ACNP criteria. Certification of Ratings of HRSD: We plan to follow the NIH protocol procedures for administration and certification of the HRSD ratings. This will include the use of a prepared script to help administer the HRSD. Certification of all raters at a participating site will be verified prior to enrollment. This will be done by shipping recordings of mock interviews (non-patient) to the sites where trained raters have determined a “gold standard HRSD score”. Site raters will then submit their scores. Following NIH procedures, large deviations will be noted, and a rater can have an additional test. This can be repeated for a total of 3 times until the site is told they must find another rater. Longitudinal Quality Control for HRSD: Following NIH procedures, to ensure that HRSD do not “drift” over time, one HRSD recording will be circulated to evaluators at all participating sites every 6 months. The evaluators will be asked to rate this recording and to return their ratings. Evaluators who drift greater than 3 points on the HRSD total score will receive telephone consultation followed by one additional HRSD recording.

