2.6 Sample Size Consideration

The primary hypothesis of the study is that in VA patients with TRMD, rTMS will result in a greater remission rate at the end of acute treatment than sham rTMS. The primary outcome measure in this study is success or failure to achieve remission from depression as defined by a score on the Hamilton Rating Scale for Depression (HRSD24) of 10 or less. The primary analysis will be done as an "intent-to-treat" analysis, i.e. patients will be analyzed in the groups to which they were randomized and drop-outs will be considered treatment failures. The primary hypothesis will be addressed using a logistic regression model with PTSD diagnosis, history of substance abuse, and site as covariates. Based on review of the studies reported in the Introduction Section, the Planning Committee felt that a 10% difference between treatments would be of clinical relevance given the severity of the illness. With a sample size of 180 per group, the proposed study will have a power of 81% to detect an absolute difference between groups of 10% in the percentage of those participants who remit (6% sham and 16% rTMS). Thus, a total of 360 patients are required. This goal of 360 patients, larger than any previous study, also provides a measure of protection should some assumptions be wrong.

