3.1.2 Analysis Conventions

This section details general policies to be used for the statistical analyses. Departures from these general policies may be given in the specific detailed sections of this statistical analysis plan. When this situation occurs, the rules set forth in the specific section take precedence over the general policies. The following policies will be applied to all data presentations and analyses.

- All statistical tests will use a significance level of $\alpha = 0.05$. Two-tailed tests will be performed for all analyses that use statistical testing.
- All p-values will be rounded to 3 decimal places. All p-values that round to 0.000 will be presented as '<0.001' and p-values that round to 1.000 will be presented as '>0.999'. Any p-value $\leq \alpha$ will be considered statistically significant.
- Summary statistics will consist of the number and percentage of responses in each category for discrete variables, and the mean, median, standard deviation (SD), minimum, and maximum for continuous variables.
- All mean and median values will be formatted to one more decimal place than the measured value. Standard deviation values will be formatted to two more decimal places than the measured value.
- All percentages will be rounded to one decimal place. The number and percentage of responses will be presented in the form XX (XX.X), where the

- percentage is in the parentheses. The decimal of the percentage may be dropped due to space constraints when creating a table.
- For a continuous variable, if it is normally distributed or approximately normally distributed, Student t test and/or the general linear regression will be performed to test the group difference as proposed in the analysis plan, otherwise, Wilcoxon test and/or a quantile regression will be used as an alternative analysis method; for a categorical variable, Pearson χ^2 test and/or a corresponding generalized linear regression will be performed to test the group difference.
 - All listings will be sorted for presentation in order of treatment group, site number, subject number, and date of procedure or event.
 - All analysis and summary tables will have the population sample size for each treatment group in the column heading.
 - Calculating change from baseline to a visit will be done as follows: change = visit –baseline.

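### Durability of remission counts the first single HRSD24 rating above 10 as recurrence, at the same cut used for entry and without confirmation, so rating fluctuation shortens apparent durability and dilutes the between-arm comparison

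*SAP*

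**What the plan says.** SAP section 3.7.1.2.1 (Durability of Remission) defines remission as an HRSD score of 10 or less. It starts the clock on the date the subject first becomes remitted and ends it on the date of recurrence. The event rule is: "If a subject is no longer remitted at a certain follow-up time point t based on the criteria, then the subject fails". A subject still remitted is censored. The arms are compared by Kaplan-Meier curves and the log-rank test (Tables and Figures 3.7.2a-c).

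The phrase about the criteria can only refer to the cut of 10, which section 2.6 also uses for the primary outcome: "as defined by a score on the Hamilton Rating Scale for Depression (HRSD24) of 10 or less". No part of the SAP adds a confirming visit, a separate recurrence threshold, a minimum change or a sensitivity analysis of this rule.

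The opening of the same section describes durability differently, as remission still present at the end of the 24-week follow-up. A patient who scores 11 at week 8 and is clearly remitted at week 24 meets that description but is failed by the event rule.

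**The concern.** Entry and failure sit on adjacent integers, and one rating decides each. HRSD is rated every four weeks in follow-up. That gives six ratings if week 24 is included; the extracted schedule in Appendix 5.2 shows five columns. A patient whose depression has not changed but whose score lies just under the cut has five or six chances to be recorded as a recurrence. Selection on one score of 10 or less also admits some patients whose usual score is above 10.

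At stake are the shape of the Kaplan-Meier curves, which would show remission lost sooner than it is, and the between-arm comparison, which would move towards no difference. The analysis would also report as recurrence something that is only the first visit at which the remission cut was not met.

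**Working it through.** **Inputs from the SAP.** Remission cut 10; 180 per arm; remission rates "6% sham and 16% rTMS"; ratings every four weeks over 24 weeks; log-rank test, two-sided 0.05. The SAP states no power, event count or hazard ratio for durability. Its only related figure is 81% power for the primary comparison. That is reproduced: with continuity correction, 176 per arm gives 81% and 181 gives 82%, so 180 fits.

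**Expected size of the durability analysis.** 180 × 0.16 = 28.8 and 180 × 0.06 = 10.8, so about 29 rTMS and 11 sham remitters, about 40 in all.

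**Assumptions (not in the SAP).** Normal, independent visit-to-visit error with SD 1 to 3 points; six visits unless stated; the same error and score distribution in both arms.

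**Step 1: a stable patient with fixed true score T.** The chance of one rating of 11 or more is p = 1 − Φ((10.5 − T)/SD). The chance of at least one in six is 1 − (1 − p)^6. For T = 9 and SD 2, p = 0.227 and 1 − 0.773^6 = 0.79. With five visits, 1 − 0.773^5 = 0.72.

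| True score | SD 1 | SD 2 | SD 3 |
|---|---|---|---|
| 6 | 0% | 7% | 34% |
| 8 | 4% | 49% | 74% |
| 9 | 34% | 79% | 89% |
| 10 | 89% | 95% | 97% |

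For T = 9 and SD 2, requiring two consecutive ratings above 10 lowers 79% to about 21%.

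**Step 2: averaged over a score distribution.** True end-of-acute scores are taken as N(20, 8) or N(15, 7), truncated at 0, with entry on one rounded score of 10 or less, no true change, and SD 1.5 to 3.

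- True remitters (true score 10 or less) failed at least once: 22% to 48% with six visits, 20% to 44% with five.
- The same patients under a two-consecutive-visit rule: 5% to 14%.
- All entrants, including those whose true score is above 10: 35% to 66% under the single-visit rule, 16% to 37% under two visits.

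**Step 3: effect on the comparison.** True recurrence is set at 6% v 12% per visit (ratio 0.50), each recurrence adding a lasting 12 points, with scores from N(20, 8). True recurrence by week 24 is 1 − 0.94^6 = 31% v 1 − 0.88^6 = 54%.

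| Population, SD | Hazard ratio, single visit | Hazard ratio, two visits |
|---|---|---|
| True remitters, SD 2 | 0.69 | 0.56 |
| True remitters, SD 3 | 0.75 | 0.59 |
| All entrants, SD 2 | 0.77 | 0.68 |
| All entrants, SD 3 | 0.84 | 0.75 |

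In true remitters the single-visit rule reports 54% v 69% recurred at SD 2 and 64% v 76% at SD 3. The two-visit rule reports 32% v 52% and 36% v 54%.

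**Step 4: power at the expected size.** This is a separate simulation with 29 v 11 remitters, true relapse of 7% v 20% per visit, and true scores uniform from 2 to 14 among those entering. Log-rank power is 67% to 69% with true relapse times. Under the SAP rule it is 52%, 40% and 31% at SD 1, 2 and 3. With two consecutive ratings, and no dropout, it is 55%, 50% and 47%.

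**The case against.** Time to the first visit outside the stated remission criterion is a coherent endpoint, and on that view the clear fault is only its label. This stands in part. Relabelling removes the false description, but the analysis still would not measure durability of remission as the section intends.

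The size is wholly assumed. A stable remitter with a true score of 6 is never failed at SD 1 and is failed 7% of the time at SD 2. This stands, and it is why ranges are given.

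A reader might take the quality-control rule in section 2.5.3.1, "Evaluators who drift greater than 3 points on the HRSD total score will receive telephone consultation", as proof that the plan tolerates a 3-point error at each visit. The SAP does not support that. The rule concerns evaluators scoring one circulated recording every six months and is a trigger for consultation. A rater who is steadily 2 points high adds no visit-to-visit variation.

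Sections 3.7.1.2.4 (remission proportions across follow-up visits) and 3.7.1.2.5 (HRSD score over time) do not make a single 11 permanent. They limit the risk of a wrong overall conclusion, but they do not correct the Kaplan-Meier curves or the log-rank test.

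Confirmation has a cost of its own. Suppose 30% of recurring patients leave after their first rise and are censored (true remitters, SD 2). The two-visit rule then reports about 25% v 38% recurred against a true 31% v 54%, which overstates durability, and its power gain is lost. This stands and shapes the remedy.

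**Conclusion.** The concern holds as a fault of definition in an additional analysis. One unconfirmed rating above the entry cut is coded as a permanent recurrence. On the assumptions shown, about 20% to 50% of stable true remitters would be failed at least once. A true ratio of 0.50 would appear as about 0.69 to 0.75 in true remitters, or 0.77 to 0.84 in all entrants, at SD 2 to 3.

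It would be tempting to conclude that noise hides any real difference in durability. The calculations do not support that: the difference is diluted and power is lost, but the direction remains. Dilution towards no difference also presumes similar error and score distributions in both arms.

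Priority is low to moderate. Durability is neither the primary outcome nor one of the five secondary outcomes in section 2.4.2, and with about 40 remitters power is limited under any rule.

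**What to change.** In section 3.7.1.2.1:

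- Keep the single-visit analysis, but name its event *first visit not in remission* and not recurrence.
- Add a prespecified confirmed-recurrence analysis: HRSD24 above 10 at two consecutive scheduled follow-up visits, dated at the first of the two. This keeps the sponsor's own cut.
- In that analysis, count a first rise followed by dropout as an event, with censoring of such patients as a sensitivity analysis. Censor only an unconfirmed rise at the final scheduled visit.
- Report both analyses side by side, and align the section's opening description of durability with the event rules.

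The cost is SAP wording and a few lines of code. The ratings are already scheduled, and section 1.0 states that the SAP precedes any analysis of the data. The downsides are fewer events, a rise at the last visit that cannot be confirmed, and some stable patients still failed when they leave after a chance rise. Entry continues to rest on one score, so part of the dilution remains: among all entrants the two-visit ratio is still 0.68 to 0.75 against a true 0.50.

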37	Adverse Events (AE) and ADE and Serious Adverse Events (SAEs) and UADE	As required														

*B= Baseline

*S= Screening

¹ Sessions 21-25 (block 5) and 26-30 (block 6) may not be required if patient goes into remission earlier

² Must be conducted within 7 days prior to randomization

³ Termination Form will be completed at the end of the study OR when a patient decides to end study participation prior to the study completion date; i.e., a patient decides to withdraw or leave the study for any reason, withdraws consent, or is suspended from the study.

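### The durability-of-remission analysis gives conflicting time origins: the named failure time is a study day, while durability and censoring are counted from remission

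*SAP*

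**What the plan says.** SAP section 3.7.1.2.1 builds the durability analysis from three consecutive statements:

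- **Failure time X_ij.** If a subject is no longer in remission at a follow-up time point, the subject counts as failed and "the failure time is the study day of failure".
- **Durability.** "Durability is calculated by subtracting the date which the subject first becomes remitted from the date of recurrence".
- **Censoring time C_ij.** For a subject still in remission, C_ij "is the date of censoring minus the study day on which the subject became remitted".

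The section continues: "Group differences will be tested based on the Log-rank test", with PROC LIFETEST named for the estimates and the test. The plotted quantity is durability: "The survival distribution of durability of remission between the two treatment groups will be plotted using Kaplan-Meier curves". Follow-up runs 24 weeks post-treatment. Results are due for the ITT, completer and fully compliant populations (Tables and Figures 3.7.2a-c).

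**The concern.** Kaplan-Meier estimation and the log-rank test need failures and censorings on one clock. Here the only quantity called a failure time is a study day, which ordinarily counts from the start of the study, while the censoring time counts from remission. The durability sentence puts failures on the remission clock but does not say that it replaces X_ij. C_ij also cannot be programmed as written, because it subtracts a study day from a calendar date.

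Two programmers could follow this section faithfully and produce different curves. If X_ij were used literally, each failure would be lengthened by that subject's time to remission and each censoring would not. Differences between arms in speed of remission would then leak into a test meant to compare durability.

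**Working it through.** The SAP gives no figure for this analysis, so there is none to reproduce. The check compares two codings: (a) both times counted from remission; (b) failures on study day, censorings counted from remission.

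**One subject.** Suppose remission in week 6 and relapse found 12 weeks later. Coding (a) gives 12 weeks. Coding (b) gives 6 + 12 = 18 weeks. A subject still in remission at 24 weeks is censored at 24 under both.

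**Inputs from the SAP.** HRSD every four weeks in follow-up (3.7.1.2.5); 24-week follow-up (3.7.1.2.1); acute phase of 4-11 weeks (Appendix 5.2); planned remission 16% and 6% of 180 per arm (2.6), so 0.16 × 180 = 28.8, about 29, and 0.06 × 180 = 10.8, about 11.

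**Assumptions, not in the SAP.** Exponential time to relapse; week of first remission r equally likely to be 4, 5, ..., 11; follow-up clock starting at remission; dropout 0% or 20%.

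**Kaplan-Meier at week 24, no dropout.** Under (a), S(t) = 2^(−t/median). With a 24-week median, S(12) = 0.707, S(16) = 0.630, S(20) = 0.561 and S(24) = 0.500. Under (b) nobody is censored before week 24, so the curve is the share with relapse time + r above 24. Relapse is found at multiples of 4 weeks. The failures counted by week 24 are therefore those found by week 20 (r = 4), by week 16 (r = 5 to 8) or by week 12 (r = 9 to 11):

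KM(24) = (1/8)(0.561) + (4/8)(0.630) + (3/8)(0.707) = 0.070 + 0.315 + 0.265 = 0.650.

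**Week 28.** Everyone censored at week 24 has left. Those still at risk are 0.650 − 0.500 = 0.150 of subjects. The share failing after week 28 is (4/8)(0.561 − 0.500) + (3/8)(0.630 − 0.500) = 0.0305 + 0.0488 = 0.079. So KM(28) = 0.650 × 0.079/0.150 = 0.34. The curve reaches 0 by week 36, because only shifted failures remain.

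Simulation with 20,000 subjects agrees closely:

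| Median durability | Week 24, one origin | Week 24, mixed | Week 28, mixed |
|---|---|---|---|
| 12 weeks | 0.25 | 0.42 | 0.21 |
| 24 weeks | 0.49 | 0.65 | 0.33 |
| 48 weeks | 0.71 | 0.80 | 0.44 |

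**Sensitivity to time of remission.** If remission came at weeks 1 to 4, the failures counted by week 24 would be those found by week 20 for every r, so KM(24) = S(20) = 0.56 against 0.50. The distortion shrinks as remission comes earlier.

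**Log-rank rejection rate with equal true durability** (24-week median, 29 against 11 remitters, two-sided 5%):

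| Time of remission by arm | Mixed coding |
|---|---|
| Same window in both arms | 5.2-5.5% |
| Days 28-63 against 42-77 | 6.0-6.1% |
| Weeks 4-6 in one arm, 6-11 in the other; 20% dropout | 8-11% |
| Active days 28-35, sham days 56-77; 20% dropout | 11.0-12.4% |

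The last scenario gave 15.1% in a run without dropout. With both times counted from remission, simulated rates were 4.3-5.6%. Under mixed coding the arm that remits sooner has earlier failures and looks less durable: in one run of the last scenario, 12.1 of the 12.4 percentage points went against the active arm.

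**The case against.** The strongest reply is that the section, read as a whole, already puts failures on the remission clock. The durability sentence follows directly on X_ij, the censoring sentence presents itself as parallel to it, and the plotted quantity is durability of remission. The section gives no origin for a study day. In the censoring formula a study day is subtracted from a date, so it seems to stand for a calendar date there. Read the same way, X_ij is just the event date, which the next sentence turns into a duration.

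Much of this stands. It is the more natural reading, and it makes any bias conditional. It does not remove the contradiction: X_ij is the only quantity called the failure time, nothing says that durability supersedes it, and C_ij is still not computable as written.

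Three stronger inferences are tempting and not supported:

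- *The trial's curve will overstate durability.* That needs literal use of X_ij, and even then the error reverses after about week 24.
- *The log-rank test has a false-positive rate of about 11%.* That needs literal coding, strongly separated remission windows and a dropout assumption. The SAP gives no basis for such a difference between arms.
- *Every recurrence is lengthened by 4-11 weeks.* That range is the length of the acute phase. HRSD is rated after each block of five sessions, and sessions 21-30 "may not be required if patient goes into remission earlier", so first remission can come before week 4 and the shift can be smaller.

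**Conclusion.** The certain defect is contradictory wording: two times for the same relapsing subject, a censoring formula that mixes a date with a study day, and no statement of which variable is analysed. The numerical consequences hold only if X_ij is coded literally beside C_ij. Even then their size depends on assumed durability, time to remission and dropout, and the log-rank distortion needs time to remission to differ between arms.

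This is a minor to moderate issue. Durability is an additional HRSD analysis, neither the primary endpoint nor one of the five secondary outcomes, and on the planning rates it would rest on about 29 + 11 = 40 remitters.

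**What to change.** In SAP section 3.7.1.2.1, delete the statement that the failure time is a study day. Define both times in days from one origin, the date the subject first becomes remitted, which the section already uses for durability:

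- X_ij = date of the first follow-up visit with HRSD24 > 10, minus the date of first remission.
- C_ij = date of the last HRSD24 assessment still in remission, minus that same date.

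Add a sentence saying that these are the times entered in PROC LIFETEST for both the Kaplan-Meier curves and the log-rank test.

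The cost is a few sentences of SAP text and no new data. The SAP says it was written before any analysis began, so the correction can be made without knowledge of results.

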3.6 Prior and Concomitant Medications

Concomitant medications are recorded every week in acute and taper treatment phases, and every other four weeks in the follow-up phase. Each summary below will be done for each treatment group and for all subjects:

- Prior medications – Prior medications are considered to be any medication that was stopped prior to the date of the randomization
- Concomitant medications – Concomitant medications are considered to be any medication that was taken on or after the date of the first dose of study drug
- All medications recorded on the CRF are coded to the therapeutic drug classes and generic drug names using the World Health Organization (WHO) drug classifications
- The current version of the World Health Organization (WHO) drug dictionary are used for the coding of medications

Each summary will give the number and percentage of subjects who took medications that were coded to each generic drug name and therapeutic drug class, as well as the number and percentage of subjects that took any medication.

Summaries for prior medications will be done for ITT medications (Table 3.6.1), while summaries for concomitant medication will be done for ITT (Table 3.6.2a), completer (Table 3.6.2b), and fully compliant (Table 3.6.2c), populations.

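### The durability clock starts at first remission but recurrence counts only at follow-up time points, so on-treatment time is failure-free by construction and the log-rank test leans toward an arm that remits earlier

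*SAP*

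**What the plan says.** SAP 3.7.1.2.1 sets out to compare how long remission (HRSD of 10 or less) lasts over the 24 weeks after treatment.

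- **Origin.** Durability is found by "subtracting the date which the subject first becomes remitted from the date of recurrence". The censoring time likewise "is the date of censoring minus the study day on which the subject became remitted".
- **Event.** "If a subject is no longer remitted at a certain follow-up time point t based on the criteria, then the subject fails".
- **Test.** "Group differences will be tested based on the Log-rank test", with Kaplan-Meier curves. No landmark, delayed entry or stratification is given.

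Three other places fix what can be observed.

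- **HRSD timing in treatment.** SAP 2.5.3.1 says the HRSD "is completed after each block of 5 sessions throughout the study", so remission can first be dated at session 5.
- **Early end of acute treatment.** Footnote 1 of Appendix 5.2 says that sessions 21–25 and 26–30 "may not be required if patient goes into remission earlier". Nothing comparable is said of sessions 6–20. The acute phase is shown as 4 to 11 weeks.
- **Taper.** The HRSD row of Appendix 5.2, as it reads in the copy at hand, has no mark in the three taper weeks and resumes at follow-up week 4. SAP 3.6 treats the taper as treatment: medications are "recorded every week in acute and taper treatment phases".

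**The concern.** The origin and the event do not cover the same period. Time starts to accrue at first remission, possibly in the first block of acute treatment, but a failure can be scored only in follow-up. HRSD ratings above 10 later in acute treatment exist in the data, yet the section gives them no role. Read as written, a patient who remits at session 5, loses remission at session 10 and regains it at session 20 is credited with unbroken remission from session 5.

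Two things follow. The curves overstate post-treatment durability by adding time in which nobody could fail. And the added time differs between arms whenever one arm remits earlier, which is plausible for rTMS if it works. Recurrences are found on a four-week grid, so a shift of a week or more re-orders failures found at the same follow-up visit, and the log-rank test responds to order.

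**Working it through.** **Plan's own figure.** The durability analysis has no design figure. The only one is 81% power for remission of 6% v 16% with 180 per arm (SAP 2.6).
- Standard error under the null: √(2 × 0.11 × 0.89 / 180) = 0.0330. Under the alternative: √((0.06 × 0.94 + 0.16 × 0.84) / 180) = 0.0326.
- Without continuity correction: Φ((0.10 − 1.96 × 0.0330) / 0.0326) = 86.1%.
- With continuity correction 1/180 = 0.0056: Φ((0.10 − 0.0056 − 1.96 × 0.0330) / 0.0326) = 82.0%, close to the stated 81%.

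This figure is not disputed. It supplies the number of remitters: 180 × 0.16 = 28.8, taken as 29, and 180 × 0.06 = 10.8, taken as 11.

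**Failure-free lead time.** With first remission at session F, last acute session E and w weeks per block of five sessions, lead = (E − F)/5 × w.
- F = 5, E = 20, w = 1: 3 weeks.
- F = E: 0 weeks.
- F = 5, E = 30, w = 1: 5 weeks.
- F = 5, E = 20, w = 11/6 = 1.83 (30 sessions in 11 weeks): 5.5 weeks.

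The earliest possible failure is therefore 3 + 4 = 7 weeks from the origin for the first patient and 4 weeks for the second. If follow-up week 4 is counted after a three-week taper, these become 10 and 7. The taper adds the same amount to both.

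**Effect on the test.** Both sets of simulations use 29 v 11 remitters with identical recurrence in both arms from the end of acute treatment, detected at follow-up weeks 4 to 24. Timing, pace and recurrence rates are assumptions; the SAP gives none.

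*Set A:* median time to relapse 16 weeks, one week per block, 2,000 trials per run (Monte Carlo standard error √(0.05 × 0.95/2000) ≈ 0.5 points). Ranges in the first three rows are over runs with and without a three-week taper and a half-week visit jitter; the last two rows are single runs. Treatment ends at session 20, or at first remission if later, except in the fourth row.

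| Mean lead, rTMS v sham (weeks) | Clock from first remission: two-sided rejection (toward rTMS) | Clock from end of acute: two-sided rejection (toward rTMS) |
|---|---|---|
| 0.65 v 0.66 | 4.9–6.8% (3.1–4.6%) | 5.2–6.5% (2.9–4.3%) |
| 0.95 v 0.37 | 5.7–7.1% (4.1–5.5%) | 5.0–6.1% (2.9–3.8%) |
| 3.0 v 0 | 9.8–11.4% (9.5–10.9%) | 4.5–6.2% (2.8–4.3%) |
| 2.65 v 1.62 (all given 30 sessions) | 6.9% (5.9%) | 5.4% (3.4%) |
| 0.36 v 0.96 (sham earlier) | 5.8% (3.5%) | 6.0% (4.1%) |

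In the 3.0 v 0 case with a three-week taper and no jitter, median durability is 22 v 19 weeks from first remission and 19 v 19 from the end of acute treatment.

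*Set B:* recurrence of 10% or 20% per four-week visit. rTMS patients first remit at sessions 5, 10, 15, 20 with probabilities 0.3, 0.3, 0.2, 0.2. Sham patients do so at sessions 5 to 30 with 0.1, 0.1, 0.2, 0.3, 0.15, 0.15, or only at sessions 20–30. Mean lead at one week per block is 0.3 × 3 + 0.3 × 2 + 0.2 × 1 = 1.7 weeks for rTMS and 0.1 × 3 + 0.1 × 2 + 0.2 × 1 = 0.7 or 0 weeks for sham, a difference of 1.0 or 1.7 weeks.
- One week per block: 6.5–7.7% rejection.
- 1.83 weeks per block: 6.7–11.3%.
- Clock from the end of acute treatment: 4.5–5.8%.
- Same timing in both arms: 5.0–5.6% from either origin.
- Mean lead difference of only 0.2 weeks: 4–6%, no different from the end-of-acute clock.

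**The case against.** **The wording can be read otherwise.** A follow-up time point might mean any later rating rather than a visit in the follow-up phase. Acute-phase scores above 10 would then count as recurrence and the lapse-and-regain example would fail. First remission might also mean the formal remission outcome at the end of acute treatment. This stands as ambiguity. But the word for first, and the tabulation of remission after each five sessions in SAP 3.7.1.2.3, favour the reading used here, and nothing in 3.7.1.2.1 selects the other.

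**Time from first documented remission is a legitimate measure.** A patient who stays well from session 5 really has been in remission longer, so rejection in the simulations is not a false positive for that quantity. This is fair as far as it goes. The section's stated aim is post-treatment durability, and it is for that aim that the rejection rate is too high. A measure from first remission would also need acute-phase relapses to count.

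**The inputs are assumed.** This stands. About 11% needs either a full three-week lead difference or the slowest pace with no sham remission before session 20. The one-sided comparator is not 2.5% either: with 29 v 11 remitters, the end-of-acute clock itself rejects about 3–4% of the time toward rTMS.

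**A reader might infer that the taper adds to the bias.** It does not. It follows acute treatment in both arms and lengthens durability without favouring either. That the HRSD is not rated in the taper rests only on empty cells in the schedule.

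**The stakes are limited.** Durability is an additional HRSD analysis, outside the primary endpoint and the five secondary outcomes, and SAP 3.7.1.2.4 examines remission through follow-up without this clock. This also stands.

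**Conclusion.** The concern holds in limited form. On the natural reading, acute-treatment time after first remission is failure-free by construction, which does not fit a post-treatment aim: 3 weeks for a session-5 remitter ending at session 20 at five sessions a week, 0 for one who first remits at the last acute session.

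When rTMS remits earlier and post-treatment recurrence is identical, two-sided rejection is about 6.5–7.5% in moderate cases and about 11% in the extreme case, against about 5% with an end-of-acute clock. Toward the earlier arm, the moderate cases give about 5–6% against 3–4%. Equal timing gives no inflation. With a mean lead difference of about 0.6 weeks, the excess is close to simulation error.

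A reader might infer that the plan is certain to favour rTMS. The document does not support that: it gives no timing, pace or recurrence figures. In the one run with sham remitting earlier, total rejection did not rise; the mean test statistic moved only slightly toward sham, from −0.07 to 0.05 (negative favours rTMS). The change is worth making because it is cheap and removes a dependence on remission speed that the section does not intend.

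**What to change.** Rewrite the time rule in SAP 3.7.1.2.1:

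- Include patients with HRSD24 of 10 or less at the end-of-acute-treatment visit. This also settles whether someone who remitted early but is not in remission at that visit enters the analysis.
- Measure both recurrence and censoring from that visit, each as a difference in dates. The section now describes failure time first as a study day and then as a duration.
- State that recurrence is the first later HRSD24 above 10.

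Optional sensitivity analyses are the same curve started at the last rTMS session, acute or taper, so that the time is truly off treatment; or time from first remission with any later HRSD24 above 10, acute-phase ratings included, counted as recurrence.

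The cost is SAP wording; the dates are already collected. Reported durations become a few weeks shorter. The main version still includes the taper, equally in both arms.
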